2.5.4. Behavioral health intervention structure and content

In the first 6 months of behavioral treatment all patients in the intervention arm received one individual orientation session and 12 individually tailored behavioral treatment sessions that included the content described below, delivered by the study staff (trained nurse or health psychologist/doctoral clinical health psychology student) described above. Patients completed the orientation session and the first intervention session for each level of behavioral intervention in-person and then had the choice of completing the subsequent sessions either in-person or by telephone. Session duration ranged from 30 to 60 min depending on treatment content and individual patient needs; patients were not charged for the behavioral intervention. All study interventionists met bi-weekly as a group with the principal investigators for supervision and consultation. The registered nurse met one-on-one weekly for supervision with the licensed clinical psychologist principal investigator. The diabetologist (i.e., primary care physician with advanced training in diabetes care) was also on-site and available for consultation and referral of patients who developed severe diabetes signs or symptoms (e.g., hypoglycemia, hyperglycemia).

2.5.5. Small changes lifestyle intervention

The Small Changes treatment sub-group included intervention arm patients with low levels of diabetes-related distress and/or depressive symptoms and the intervention focused on lifestyle modifications to improve diabetes and mood based on the Small Changes health behavior change model [12] as we have previously described [11], as well as American Diabetes Association (ADA) [10] recommended diabetes education topics of healthy eating, being active, monitoring, taking medication regularly, healthy coping, and decreasing risks. The Small Changes model encourages health behavior change and maintenance through the use of incremental goals over time that are self-selected by patients and relative to their baseline. The Small Changes approach has been shown to be more effective for weight loss than traditional treatment in a health care setting with Veterans [13]. Small Changes lifestyle intervention sessions were delivered by a nurse trained in behavior change and focused on the development of self-management strategies and the setting of SMALL (specific, measurable, action-oriented, linked-to-your-life, and long-term) goals. Patients were instructed to self-monitor and record daily fasting finger stick blood sugar (FSBS), weight, mood, medication taking, and selected nutritional intake (using only check marks) using the provided calendar and scale as well as their daily steps with pedometers provided by the study. Nutritional monitoring and goal setting was based on a Stop Light Guide [14] which was adapted for diabetic populations. In this modified system, food and beverage items were categorized as “Green” (high nutrient value, little effect on glycemic control), “Yellow” (high nutrient value, moderate effect on glycemic control), and “Red” (low nutrient value, large effect on glycemic control). While patients were introduced to the full modified Stop Light Guide, patients were instructed only to monitor how many red foods they were eating daily and make relative nutritional changes to their daily baseline consumption of “Red Foods”. Specifically, patients checked-off daily servings of Red Foods in five categories (breakfast, lunch, dinner, snacks, and beverages) in order to get a daily total of Red Food servings (sum from these five categories) and then set goals to reduce their daily total throughout the course of treatment. Monitoring and goal setting was designed in this manner to reduce monitoring burden and to increase the patient's focus on food and beverage items with potential for substantial adverse impact on weight and glycemic control.

2.5.6. Cognitive behavioral therapy

The Cognitive Behavioral Therapy (CBT) subgroup focused on the reduction of depressive and/or diabetes-related distress symptoms through modification of negative thoughts and problematic behaviors as well as improvement of diabetes self-management strategies. CBT combines cognitive therapy, which targets maladaptive thinking that impacts emotions and behavior with behavioral therapy which directly targets the behaviors which impact mood. CBT intervention components were guided by two evidence-based treatment manuals [15,16] as well as an evidence-based manual [17] for behavioral activation. Session content utilized cognitive techniques to identify and challenge general and diabetes-specific cognitive distortions that result in maladaptive behavior; and behavioral techniques including behavioral activation and specific behavior change related to diabetes and/or mood (self-monitoring, sleep hygiene, eating habits etc.). Patients were taught behavioral strategies to become re-engaged in pleasant activities (behavioral activation) as well as cognitive techniques to identify and then challenge cognitive distortions that result in negative automatic thoughts and subsequent maladaptive

behavior. These sessions occurred in 50 min face-to-face (in private therapy rooms in the primary care clinic) or via telephonic visits with the health psychologist/student. Problem-solving strategies were utilized as needed to assist with behavioral goals related to mood and diabetes management.

CBT Therapy was also tailored to individual patient needs. For patients who met criteria for this subgroup but who had more intermediate levels of depressive or distress symptoms, the health psychologist utilized Problem Solving Therapy (PST), a variant of CBT which focuses on facilitation of effective coping and adaptive problem-solving skills [18]. Problem Solving Therapy has been shown to be an effective intervention strategy for improvement in both diabetes specific outcomes and depression [19,20], particularly in patients with lower socioeconomic status and diabetes [21]. Problem Solving Therapy has also been adapted for delivery in primary care settings (PST-PC) as a brief form of evidence-based psychotherapy [22] and is supported by randomized controlled studies in primary care settings [23]. Patients receiving CBT involving PST began treatment by compiling a personalized on-going list of “problems” or areas for potential improvement based on ADA recommended [10] diabetes topics. In each session, the patient chose a problem from his or her list to address and used the following steps: 1) problem definition, 2) establishment of realistic goals for problem resolution, 3) generation of multiple solution alternatives, 4) determination of the pros and cons of solution alternatives 5) evaluation and solution choice, 6) implementation of the preferred solution, and 7) evaluation of the outcome. Additionally, patients were provided education about behavioral activation for mood improvement and were assisted with setting goals to increase engagement in pleasurable activities for improved mood. Primary care providers for patients in the intervention arm were offered consultation with the diabetologist and, when needed, consultation with a clinical pharmacist to optimize medical management. Primary care providers were instructed to titrate medication dosages to appropriate therapeutic dosages based on finger-stick blood sugar response and subsequent HbA1c values. Patient response, adherence, and potential for side effects were monitored regularly by the nurse care manager during face-to-face and telephone follow-up, with particular attention to the potential for hypoglycemia associated with insulin and sulfonylurea drugs.

2.5.7. Community based support of the intervention

All intervention patients had access to a trained Community Health Worker (CHW) who had extensive experience promoting healthy behaviors for chronic disease management in the targeted region. This CHW component of the intervention was designed as culturally relevant peer support and as a navigator to community resources that helped patients address logistical challenges to implementing healthy behaviors, problem solving, and accessing healthy food/activity in the target community. The CHW contacted each intervention patient by phone approximately quarterly and offered logistical and navigational support as well as encouragement for behavioral change.

2.5.8. Usual care group (control)

Patients in the control group received the educational materials described above (i.e., Living with Diabetes book) and continued to receive usual care at their primary care provider's office.

2.5.9. Overall study evaluation

The authors evaluated the effectiveness of this stratified integrated behavioral health model on diabetes related distress, depressive symptoms, and diabetes outcomes (see measures below) at 6- and 12-month follow-up visits. It was hypothesized that the collaborative behavioral health intervention would produce greater improvement in diabetes related distress, depressive symptoms, as well as HbA1c at 6 and 12 months vs. usual care. A priori analyses were also designed to evaluate mediators of the relationship between improvement in psychological measures (distress/depression) and improvement in HbA1c with the hypothesis that the intervention-associated improvements in diabetes-related distress, regimen related distress, and depressive symptoms would be associated with improvements in A1c in part via association with improvements in self-care behaviors.

2.5.10. Mid-study Re-assessment and maintenance treatment

At the 6-month mid-study assessment, all patients were re-evaluated using the same measures described below, and either continued to receive twice monthly behavioral sessions (for those with no improvement in distress and depressive symptom scores) as originally assigned at the initial orientation visits, or were transferred to once per month telephonic maintenance follow-up care (for those whose distress and depressive symptom scores improved). Maintenance treatment reinforced prior intervention strategies that produced benefit and provided lifestyle behavioral counseling using elements of the small changes model described above) by the nurse care manager.

2.6. Biological and psychosocial measures

Patients in both intervention and control groups completed a demographic questionnaire [age, gender, race (African American, Caucasian, other), highest education level completed (high school or less, some college, college degree, any graduate education), marital status (single, married, separated, divorced, widowed), annual household income (\$ < 40,000/yr. vs. \geq \$40,000/yr.) duration of diabetes (yrs.; self-reported), number of doctor visits in the last 12 months] at baseline; biological and psychosocial assessments were completed at baseline, 6, and 12 months. Weight was obtained using an EatSmart Precision Plus Bathroom Scale model ESBS-05. Height was measured using a wall stadiometer. Blood pressure was obtained using an Omron Intellisense Automatic BP Monitor model BP760 (Omron, Inc., Chicago, IL) using a standardized protocol. All patients were seated for five minutes with both feet on the floor, and with their arm supported. Blood pressure was measured twice and averaged. HbA1c was measured by fingerstick using the Siemens Medline DCA Vantage 2000 HbA1c Reagent Kit. The study utilized previously validated psychosocial measures including the Patient Health Questionnaire (PHQ-9), Diabetes Distress Scale (DDS-17), and the Satisfaction with Life Scale with data collected at baseline, 6-months, and 12-months. The PHQ-9 is a nine-item self-report measure [24] intended for use in primary care settings to assess symptoms of depression. Scores can be summed to indicate, minimal, mild, moderate, or severe depressive symptoms. The

DDS-17 is a 17-item self-reported measure [4] which is designed to indicate a respondent's level of current emotional distress related to diabetes management. Scores are summed and divided by 17 (i.e., mean score) to categorize distress as low, moderate, or high. The DDS-17 also has four subscales, including the Regimen Related Distress sub-score which is an average from five items that assess distress associated with specific treatment and monitoring activities, and which has been correlated with diabetes outcome measures [6,9]. The Satisfaction with Life Scale [25] is a 5-item self-report measure designed to assess satisfaction with a respondent's life as a whole. The study also utilized several previously validated health behavior measures including the Diabetes Empowerment Scale, The Summary of Diabetes Self-Care Activities Measure (SDSCA), the Rapid Eating Assessment for Participants – Shortened Version (REAP-S), and the Duke Activity Status Index, with data collected at baseline, 6-months, and 12-months. The Diabetes Empowerment Scale-Short Form [26] is an abbreviated self-report measure of diabetes-related psychosocial self-efficacy. Dietary habits were assessed using the REAP-S, a 16-item self-report survey [27] designed for use in primary care to directly assess dietary habits for patients with diabetes. Physical activity was assessed by the Duke Activity Status Index, a 12-item self-report measure [28] to assess functional capacity.

2.6.1. Data analysis plan

All data was collected by project staff via in-person interviews/assessments at all time points and entered into a REDCap database. Demographic and baseline data will be compared between treatment groups; co-variates will be used for any significant differences on subsequent analyses. The principal outcome measure, change in HbA1c, and secondary outcome measures (e.g., change in DDS-17 score, PHQ-9 score, etc.) from baseline to 12 months of follow-up, will be compared (intervention group vs. usual care group) using Students t-test or analysis of variance (ANOVA) as appropriate. The correlation between change in HbA1c and changes in other factors such as DDS-17 score, PHQ-9 score, Diabetes Empowerment Scale Score, etc. will be examined using Pearson Correlation Coefficient. Where appropriate, multivariate analyses including general linear models will be used to further examine the relationship between changes in psychosocial variables and change in HbA1c, (e.g., change in depression or distress and relationship to change in HbA1c) while controlling for demographic characteristics and baseline values. In addition, based on our previous work [11], analyses examining treatment outcomes based on insulin use between the treatment and control groups will be conducted using Students t-test or repeated measures ANOVA. Furthermore, exploratory analyses, including multiple linear regressions, will be examined in the treatment intervention group to examine potential mechanisms for change across time. Missing data at follow-up associated with patients missing assessments will be addressed by using multiple imputations to replace missing values. All variables with <20% of randomly missing data will be kept and imputed. Multiple imputation is preferred because it is superior to other missing data approaches (i.e. mean replacement, last observation) and removing patients with missing data from the study (i.e. list-wise) which would result in a significant loss of the study sample. All analyses will be conducted using SPSS vs. 24 (IBM, Armonk, New York).

REFERENCES

[1] L.E. Barker, K.A. Kirtland, E.W. Gregg, L.S. Geiss, T.J. Thompson, Geographic distribution of diagnosed diabetes in the United States: a diabetes belt, *Am. J. Prev. Med.* 40 (4) (2011) 434–439.

[2] A. Pan, M. Lucas, Q. Sun, et al., Bidirectional association between depression and type 2 diabetes mellitus in women, *Arch. Int. Med.* 170 (21) (2010) 1884–1891.

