2.3. Study population and setting

The study was specifically targeted at patients with uncontrolled T2D who also reported either depressive symptoms and/or symptoms of diabetes-related distress, as measured by previously validated instruments (see below). In our prior pilot work in this same region using the same instruments [11], 40% of patients screened positive for diabetes related distress and 21.5% reported elevated depressive symptoms. The study took place in an academic Family Medicine clinic setting that included a residency program located in the southeastern U.S.

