2.3.1. Screening

The population screened for this study included: adult patients (18 to 75 years of age) who had established care at the academic primary care practice (at least one visit in the last 12 months) and who had an electronic medical record established diagnosis of T2D and a recent (< 12 mo.) HbA1c that reflected inadequate glycemic control ($\text{HbA1c} \geq 7.0$). Exclusion criteria for screening included a medical record established diagnosis of advanced disease (e.g., end stage renal disease, advanced heart failure, blindness, metastatic cancer) or the presence of alcoholism, cognitive impairment, or major psychiatric disease that would preclude active participation. Individuals who met preliminary eligibility were contacted by the study coordinator and invited to be seen for a study-specific visit or was screened following a regular provider visit. At the time of placement into an examination room for the study visit, a statement of informed consent and HIPPA consent was carefully reviewed with each potential participant. A two-item version of the Diabetes Distress Scale (DDS-2) and the two-item version of the Patient Health Questionnaire (PHQ-2) was then administered as a screening instrument by office staff. These 2-item versions have excellent sensitivity (95% and 97%, respectively), and are defined in greater detail below in the outcome measures section. Study staff collected the completed measures and scored them. If the score on either measure was considered positive (mean score > 3 on DDS-2; total score > 3 on PHQ-2), the individual was assessed regarding glycemic control. A screening fingerstick HbA1c test was obtained while the patient was in the examination room and evaluated using a Siemens analyzer [DCA Vantage portable analyzer, Siemens Medical Solutions, Malvern, PA] as described below. If the patient met all the screening criteria described above, had a HbA1c value that day that was > 7.0 , and also had positive co-morbid behavioral symptoms (depressive and/or diabetes-related distress symptoms on one or more of the 2 item screening instruments), then he/she was scheduled for an enrollment visit into the study. Once enrolled, the patient completed the full DDS-17 and PHQ-9 plus additional baseline instruments that are defined below and was then scheduled for a study orientation visit.

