2.5.3. Initial assessment of co-morbid behavioral symptoms and severity stratification

Once randomized at the orientation visit, patients in both groups completed a full battery of measures which are detailed below. The full psychological measures [Patient Health Questionnaire-9 (PHQ-9) for depressive symptoms and the Diabetes-related Distress-17 (DDS-17) scales for diabetes-related distress symptoms], were promptly scored by study staff and used to triage or stratify patients into one of two appropriate evidence-based behavioral interventions based on the severity of symptoms of depression or distress [(Small Changes Lifestyle Coaching if PHQ-9 < 10 and/or mean DDS-17 < 3) or Cognitive Behavioral Therapy (CBT; PHQ-9 \geq 10 and/or mean DDS-17 – \geq 3.0)]. Based on these two measures, it was possible to have patients with only depressive symptoms, only diabetes-related distress symptoms, or a combination of both distress and depressive symptoms. This complex design was specifically chosen for pragmatic reasons related to: 1) insuring generalizability in primary care where patients with uncontrolled diabetes frequently have either or both of these co-morbidities, and 2) to explore whether evidence-based but tailored treatments would relieve varying levels of symptoms of diabetes-related distress and/or depression and facilitate diabetes control when delivered in this integrated care fashion in the context of a busy primary care practice. The proposed stratification design may also have the potential to be more efficient and cost-effective than providing a potentially suboptimal level of intervention for a period of time before intensifying treatment as might occur in a standard stepped care model. Therefore, the behavioral intervention was designed to pilot test a severity-stratified behavioral treatment model with patients being triaged at baseline to one of three levels of behavioral intervention (small changes lifestyle coaching, or one of two levels of cognitive behavioral therapy), each paired with guideline informed standard medical care delivered by the patient's primary care provider with available consultative support from the study's diabetologist to assist with medication selection and monitoring. All three levels of behavioral health intervention had the overarching goal of improving the patient's glycemic control (i.e., HbA1c) as well as improving depressive and/or distress symptoms.

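### PHQ-9 and DDS-17 change are compared between whole arms with no baseline score and no planned estimate for symptomatic patients, although one positive screen is enough for entry

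*Combined protocol and SAP*

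**What the plan says.** Section 2.3.1 sets the entry rule. A patient goes forward "If the score on either measure was considered positive", and the closing condition repeats that one instrument suffices: "depressive and/or diabetes-related distress symptoms on one or more of the 2 item screening instruments". Section 2.5.3 acknowledges the consequence: "it was possible to have patients with only depressive symptoms, only diabetes-related distress symptoms, or a combination of both". It says that this mix was intended, for generalizability in primary care.

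Section 2.5.9 states the hypothesis without restriction by baseline symptom: "the collaborative behavioral health intervention would produce greater improvement in diabetes related distress, depressive symptoms, as well as HbA1c" at 6 and 12 months, against usual care.

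Section 2.6.1 gives the test: "secondary outcome measures (e.g., change in DDS-17 score, PHQ-9 score, etc.) from baseline to 12 months of follow-up, will be compared", intervention against usual care, by Student's t-test or ANOVA. Four other provisions in that section come close but do not fill the gap:
- Covariates enter only where the arms differ significantly at baseline.
- The general linear models that control for baseline values concern the relation between psychosocial change and HbA1c change, not the arm comparison.
- The exploratory regressions on mechanisms are confined to the intervention group.
- The only subgroup named is insulin use.

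Section 2.6.1 does not name an all-randomized set. That reading follows from an unrestricted arm comparison with missing follow-up imputed.

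**The concern.** A patient admitted for distress alone will usually start with a lower PHQ-9 than one admitted for depressive symptoms, and so has less room to improve. The same applies to DDS-17 in patients admitted for depressive symptoms alone. The whole-arm mean change mixes these patients with those who have the symptom. If the former gain less, the mean is smaller than the effect in symptomatic patients, and a null result has two explanations that the planned analysis cannot separate: no effect, or an effect averaged away. A subgroup estimate added after the data are seen would carry little weight.

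Separately, an unadjusted comparison of change does not use the baseline score efficiently, although that score is collected from everyone.

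**Working it through.** **The plan's own figure.** Section 2.4 gives about 50 per arm for a 0.7 difference in HbA1c change, alpha 0.05, power 0.80. No SD is stated, so the figure can only be solved backwards. Setting n = 2(1.96 + 0.84)² SD²/0.7² = 50, two-sided, gives SD = 1.25, a standardized effect of 0.56. No effect, SD or power is given for PHQ-9 or DDS-17.

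**Share entering without the symptom.** Inputs from Section 2.3: "40% of patients screened positive for diabetes related distress and 21.5% reported elevated depressive symptoms". Write D = 0.40, P = 0.215, and B for the share with both, which is not given. Share of entrants without a positive depression screen = 1 − P/(D + P − B); without a positive distress screen = 1 − D/(D + P − B).

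| Overlap assumed | B | D + P − B | No positive depression screen | No positive distress screen |
|---|---|---|---|---|
| All depressed also distressed | 0.215 | 0.400 | 46% | 0% |
| Independent | 0.086 | 0.529 | 59% | 24% |
| No overlap | 0 | 0.615 | 65% | 35% |

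The depression figure falls below 50% only if D + P − B < 2P = 0.43. That means B > 0.185, or more than 0.185/0.215 = 86% of depressed patients also distressed.

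**Dilution.** Let f = P/(D + P − B) be the depression-positive share (0.54, 0.41, 0.35), and r the effect in screen-negative patients as a fraction of the effect in screen-positive patients. The whole-arm effect is the effect in positives times f + (1 − f)r. At r = 0 the factor is 0.54, 0.41 or 0.35. At r = 0.5 it is 0.77, 0.70 or 0.68.

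**Illustrative power.** Assume a standardized effect of 0.56 in screen-positive patients (borrowed from the HbA1c back-calculation), equal SDs, 50 analysed per arm, two-sided 5%, normal approximation.

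| f | Whole arm, r = 0 | Whole arm, r = 0.5 | Whole arm, r = 1 | Positives only (50f per arm) |
|---|---|---|---|---|
| 0.54 | 0.325 | 0.576 | 0.800 | 0.537 |
| 0.41 | 0.205 | 0.503 | 0.800 | 0.430 |
| 0.35 | 0.164 | 0.472 | 0.800 | 0.381 |

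The two tests break even where f + (1 − f)r = √f, that is r = √f/(1 + √f): 0.42, 0.39 and 0.37. Below that the positives-only test has more power; above it the all-patient test does.

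**Gain from the baseline score.** With equal variance σ² at both visits and correlation ρ between them, the change score has variance 2σ²(1 − ρ) and the baseline-adjusted outcome σ²(1 − ρ²). The ratio is (1 + ρ)/2. For assumed ρ of 0.3, 0.5 and 0.7 it is 0.65, 0.75 and 0.85, a 15% to 35% reduction in variance in the all-patient comparison.

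**Size of the symptomatic group.** At 50 analysed per arm, 50 × 0.35 to 50 × 0.54 is about 18 to 27 per arm by depression screen.

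**Timing of the full scales.** Section 2.3.1 has the full PHQ-9 and DDS-17 completed at enrollment, before the orientation visit is scheduled. Section 2.5.3 has them completed once patients are randomized at that visit. Section 2.4 places randomization at the start of that visit, and Section 2.2 says the trial is not blinded. The two-item screens come before randomization on either account.

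**The case against.** A reader might infer that the whole-arm comparison is wrong and should give way to tests confined to patients with PHQ-9 ≥ 10 or DDS-17 ≥ 3.0. The documents do not support that, for five reasons:
- The population was mixed on purpose and the hypothesis in Section 2.5.9 is unrestricted, so the all-patient contrast is a valid, unbiased answer to the question asked.
- The power advantage of a subset test needs r below about 0.37 to 0.42, and no section gives r. A negative screen is not a score at the floor: Section 2.6 describes graded PHQ-9 severity.
- The 46% to 65% describes two-item screen status. The number with PHQ-9 ≥ 10 cannot be derived, and the Small Changes level in Section 2.5.3 expects entrants with low full-scale scores.
- If Section 2.5.3 has the order right, selecting on the full scales would select on self-report given after allocation could be known.
- The subset is small, with illustrative power of only 0.381 to 0.537.

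The top of the range is also doubtful. The Introduction says distress can be associated with depressive symptoms, and a positive association gives about 46% to 59%. The pilot's overlap, cut-offs and glycemic mix are not given, and the reference list describes it as a trial in African American women, a narrower population.

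All of this stands against replacing the test. None of it supplies the missing baseline adjustment or the missing estimate for symptomatic patients.

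**Conclusion.** The gap is real and modest. For two secondary outcomes, the arm comparison uses no baseline score unless the arms happen to differ significantly on it, and nothing is prespecified by symptom status. On the pilot rates, 46% to 65% of entrants would lack a positive depression screen and 0% to 35% a positive distress screen, so PHQ-9 is affected more than DDS-17.

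The understatement of the effect in symptomatic patients rests on the assumption that screen-negative patients improve less. Its size, a factor of 0.35 to 0.54 at r = 0 and 0.68 to 0.77 at r = 0.5, cannot be fixed from the documents, and the power figures are illustrations only. What holds without knowing r is that the planned analysis gives no separate answer for symptomatic patients. This is a cheap improvement to the analysis, not the correction of a biased one, and it does not touch the HbA1c primary analysis.

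**What to change.** In Section 2.6.1:
1. Keep the all-patient comparison as the main test for PHQ-9 and DDS-17, fitted as a linear model with arm and baseline score in place of the unadjusted t-test on change.
2. Prespecify, as supportive, the same model with an arm-by-baseline-score interaction, and report the arm difference with its confidence interval at the average baseline score of symptomatic patients. State that this neither replaces the main test nor equals a subset test: it estimates the effect at a chosen baseline value and assumes linearity.
3. Define symptomatic as positive on the pre-randomization screen (PHQ-2 for PHQ-9, DDS-2 for DDS-17). Use PHQ-9 ≥ 10 and DDS-17 ≥ 3.0 only if Sections 2.3.1 and 2.5.3 are reconciled to show that the full scales were completed before allocation was known. If they were not, use the screening score in the interaction as well.

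The cost is SAP wording and two extra model terms per outcome on data already collected, a linearity assumption, and an imprecise supportive estimate (about 18 to 27 symptomatic patients per arm for PHQ-9 at 50 analysed per arm, by screen status).
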